### 8.3.1 Baseline (Visit 2)

**Note: it must be ensured that inclusion criteria regarding the severity of the disease remain relatively unchanged since screening in order to exclude patients responding to the emollient use since screening visit i.e. IGA score must be unchanged and EASI score should not change by more than 10%.** Patients will attend the investigational site at Visit 2 when the following procedures/assessments will occur.

- Verification of inclusion/exclusion criteria (Sections 7.2 & 7.3)
- Patient Randomisation (as detailed in Section 10.5)
- Samples for clinical laboratory safety tests (haematology and serum biochemistry as detailed in Section 9.2.4)
- Pharmacokinetic Sampling (as detailed in Section 9.2.9)
- Biomarker Sampling (as detailed in Section 9.2.10)
- Vital signs (blood pressures, heart rate and body temperature), as detailed in Section 9.2.3);
- Physical examination (as detailed in Section 9.2.2)
- Electrocardiogram (ECG) (as detailed in Section 9.2.7)
- Dispense Study Drug
- Dispense Patient Compliance Log
- Body Surface Area (as detailed in Section 9.1.4)
- Validated Investigator's Global Assessment (as detailed in Section 9.1.1)
- Eczema Area and Severity Index (EASI) (as detailed in Section 9.1.2)
- NRS Pruritus assessment (as detailed in Section 9.1.3)
- Dermatology Life Quality Index (DLQI) Questionnaire (as detailed in Section 9.1.5)

- Patient Orientated Eczema Measure (POEM) questionnaire (as detailed in Section 9.1.6)
- SCORing AD (SCORAD) questionnaire (as detailed in Section 9.1.7)
- Athens Insomnia Scale (AIS) (as detailed in Section 9.1.8)
- Patient- Orientated SCORAD questionnaire (as detailed in Section 9.1.9)
- Concomitant medication assessment (as detailed in Section 9.2.13)
- Review emollient usage and capture
- AE assessment (as detailed in Section 11)

If all study entry criteria are satisfied the Investigator will randomize the patient and provide the patient with the DS107 capsules or placebo capsules from one of the patient treatment packs available at the site (allocated via the central randomization).

The first administration of DS107 or placebo will be carried out after the Baseline visit. Following this DS107 capsules or placebo medication will be administered once daily. IMP will be administered approximately 2 hours after food consumption at the same time each day. Patients will be instructed to not consume food for approximately 1 hour after IMP administration.

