### 8.3.6 Week 16 (Visit 7) / End of Treatment or Early Termination

Patients will return to the investigational site at Visit 7. **The last dose of DS107/placebo should be taken the day before Visit 7.**

For accountability purposes, patients will be required to bring both the used DS107/Placebo patient packs and unused DS107/Placebo supplied at Visit 6. Patients will be required to provide the patient compliance log for confirmation of compliance.

The following procedures/assessments will occur:

- Samples for clinical laboratory safety tests (haematology and serum biochemistry as detailed in Section 9.2.4)
- Pharmacokinetic Sampling (as detailed in Section 9.2.9)
- Biomarker Sampling (as detailed in Section 9.2.10)
- Sample for pregnancy test (only female patients of child-bearing potential, as detailed in Section 9.2.5)
- Vital signs (blood pressures, heart rate and body temperature), as detailed in Section 9.2.3);
- Physical examination (as detailed in Section 9.2.2)
- Electrocardiogram (ECG) (as detailed in Section 9.2.7)
- Body Mass Index (as detailed in Section 9.2.8)
- Collect Study Drug
- Collect and Review Patient Compliance Log
- IMP Accountability (as detailed in Section 10.6)
- Body Surface Area (as detailed in Section 9.1.4)
- Validated Investigator's Global Assessment (as detailed in Section 9.1.1)
- Eczema Area and Severity Index (EASI) (as detailed in Section 9.1.2)
- NRS Pruritus assessment (as detailed in Section 9.1.3)
- Dermatology Life Quality Index (DLQI) Questionnaire (as detailed in Section 9.1.5)
- Patient Orientated Eczema Measure (POEM) questionnaire (as detailed in Section 9.1.6)
- SCORing AD (SCORAD) questionnaire (detailed in Section 9.1.7)
- Athens Insomnia Scale (AIS) (as detailed in Section 9.1.8)
- Patient- Orientated SCORAD questionnaire (as detailed in Section 9.1.9)
- Concomitant medication assessment (as detailed in Section 9.2.13)
- Review emollient usage and capture
- AE assessment (as detailed in Section 11)

The DS107 or placebo patient packs will be returned. No further DS107 or placebo patient packs or patient compliance logs will be issued. Following completion of the study assessments at this visit, there will be continued study restrictions in line with those described in Sections 9.2.12.

An NRS for the assessment of pruritus will continue to be captured on a daily basis from screening to the follow up visits. Emollient use will also continue to be captured on a daily basis for the same period.

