#### 10.6 Drug Accountability

All IMP supplies for this study must be retained in a safe place at all times of the study. Only personnel authorised by the principal Investigator at each site should dispense the IMP and the

accountability is the responsibility of the Investigator. The Investigator or pharmacist must complete the IMP supply form, verifying the receipt of IMP. The patients should return all used and unused packs of IMP to the study site at every visit. Following compliance assessment the packs of IMP will be retained in a secure location at the site until the end of the study. After the Clinical Research Associate (CRA) has completed a final drug accountability review, the IMP may be returned or destroyed only when instructed by the CRA.

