## 4 Data Handling

### 4.1 General

#### 4.1.1 Data sources

Most of the data collected in connection with this trial are recorded in an eCRF (electronic Case Report Form). The diary data (NRS, AIS, IMP compliance etc) is recorded in the IRT system. All patient data will be entered by the investigator. Details can be found in the data handling manual for this study. The entered data are subjected to plausibility checks. These are detailed in the data validation plan for this study.

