#### **4.2.13 Study medication: Intake and duration of intake**

The duration of intake of study medication will be calculated as day of last dispensed of study medication minus day of first dispensed of study medication plus one.

The intake of study medication will be calculated as the number of capsules dispense per visit.

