### Study medication

- Duration of intake of study medication [days]
- Number of capsules dispense

will be analysed as described in chapter 6.2 with the Safety Analysis Set.

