14.2.2.6.13	Change in PO-SCORAD score at follow-up (MMRM)	FAS	Change from week 16 in PO-SCORAD score to week 18 and 20	T8.1 T8.2
14.2.2.6.14	PO-SCORAD (Value, Change from Baseline, Change from Wk 16) by visit	FAS	Descriptive statistics by visit	T3a
14.2.3	Further Analyses			
14.2.3.1	Previous medication	SAS	Descriptive statistics by ATC classification (level 1 and 2 and preferred term)	T10
14.2.3.2	Concomitant medication	SAS	Descriptive statistics by ATC classification (level 1 and 2 and preferred term)	T10
14.2.3.3	Reason for Termination	Enrolled Set	Frequency Table	T4
14.2.3.3.1	Reason for Termination	SAS	Frequency Table	T4
14.2.3.4	Screening failure	Non-randomised subjects of the Enrolled Set	Frequency Table	T4
14.3	Safety			
14.3.1	Study medication			
14.3.1.1	DS107 intake duration	SAS	Descriptive statistics	T3
14.3.1.2	Capsules	SAS	Descriptive statistics of number of capsules dispensed	T3
14.3.2	Adverse events			
14.3.2.1	Summary table of Adverse Events	SAS	Frequency table of patients and number of events per AE category	T11
14.3.2.2	Adverse Events by MedDRA SOC and preferred term	SAS	Frequency table	T12

14.3.2.3	Serious Adverse Events by MedDRA SOC and preferred term	SAS	Frequency table	T12
14.3.2.4	AEs related to DS107 by MedDRA SOC and preferred term	SAS	Frequency table	T12
14.3.2.5	AEs leading to study discontinuation by MedDRA SOC and preferred term	SAS	Frequency table	T12
14.3.2.6	AEs by SOC, PT and worst intensity	SAS	Frequency table	T13
14.3.2.7	AEs by SOC, PT and outcome	SAS	Frequency table	T13
14.3.2.8	SAEs by SOC, PT and outcome	SAS	Frequency table	T13
14.3.2.9	Most frequent non-serious adverse events by MedDRA SOC and preferred term	SAS	Frequency table	T13
14.3.5	Vital signs			
14.3.5.1	Vital signs	SAS	Descriptive Statistics	T3a
14.3.5.2	Change in vital signs from baseline	SAS	Descriptive Statistics	T3a
14.3.5.3	ECG	SAS	Descriptive Statistics	T4a
14.3.6	Laboratory values			
14.3.6.1	Clinical Chemistry & Haematology	SAS	Descriptive Statistics	T3a
14.3.6.2	Clinical Chemistry & Haematology per category	SAS	Frequency Table (number and percentage of patients with normal values, abnormal values with clinical significance and abnormal values without clinical significance)	T4a
14.3.6.3	Change in Clinical Chemistry & Haematology	SAS	Shift Table	T14
14.3.7	Physical Examination			

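### SAP 4.2.13 derives duration of intake from dispensing dates, so an on-schedule 16-week completer is tabulated as 85 days instead of 112

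*SAP*

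**What the plan says.** SAP 4.2.13 (Study medication: Intake and duration of intake) gives two rules. Duration of intake is "calculated as day of last dispensed of study medication minus day of first dispensed of study medication plus one". For quantity, "The intake of study medication will be calculated as the number of capsules dispense per visit". SAP 7.6 (Study medication) summarises both in the Safety Analysis Set. In SAP section 8, duration goes to Table 14.3.1.1 and the capsule count to Table 14.3.1.2, which is described as "Descriptive statistics of number of capsules dispensed".

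The protocol fixes when drug is handed out and when it is taken:

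- The flow chart (Appendix 1) marks dispensing at Baseline, Week 4, Week 8 and Week 12, which are Days 0, 28, 56 and 84. Week 16 is Day 112.
- Section 8.3.1: "The first administration of DS107 or placebo will be carried out after the Baseline visit".
- Section 8.3.6, for Week 16: "No further DS107 or placebo patient packs or patient compliance logs will be issued". The same section, and footnote 4 of the flow chart, put the last dose on the day before the Week 16 visit.
- Section 10.4 sets the treatment period at 16 consecutive weeks of once-daily dosing.

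Dose-level data are collected. Protocol 8.3 has every self-administration entered in a compliance log. SAP 4.1.1 states: "The diary data (NRS, AIS, IMP compliance etc) is recorded in the IRT system". Protocol 10.6 adds: "The patients should return all used and unused packs of IMP to the study site at every visit".

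**The concern.** A dispensing date marks the start of a supply interval, not its end. Subtracting the first dispensing date from the last counts every interval except the final one, which at Week 12 is four weeks of dosing. The label in Table 14.3.1.1 promises duration of intake. The formula delivers the time between the first and last hand-out of drug.

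This table is the only planned summary of how long patients were treated. The rationale in protocol section 3 is that 16 weeks may show more than the 8 weeks studied in the two earlier efficacy trials. A table showing about 12 weeks for patients who took all 16 would misstate the feature that sets this trial apart. Because the variable can take only as many values as there are dispensing visits (apart from visit-window variation), it also cannot show when within an interval a patient stopped.

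**Working it through.** **Inputs.** Dispensing days 0, 28, 56, 84 and Week 16 on Day 112 (protocol Appendix 1). No dispensing at Week 16, and last dose the day before it (protocol 8.3.6). First dose after the Baseline visit (protocol 8.3.1), taken here as Day 0. Visit windows of ±2 days (Appendix 1).

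**The plan's own figure.** 16 weeks × 7 = 112 days. From the dosing rules, last dose day − first dose day + 1 = 111 − 0 + 1 = 112. The two agree.

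**The SAP formula, on-schedule completer.** Last dispensing day − first dispensing day + 1 = 84 − 0 + 1 = 85. Shortfall: 112 − 85 = 27 days, and 27/112 = 24.1%.

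**If the first dose is on Day 1.** The protocol says only that it follows the Baseline visit. Days dosed: 111 − 1 + 1 = 111. The SAP figure stays at 85. Shortfall: 111 − 85 = 26 days, and 26/111 = 23.4%.

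**Patients who stop early** (on schedule, first dose Day 0, no further dispensing after stopping):

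| Last dose on Day | Days dosed | SAP 4.2.13 |
|---|---|---|
| 13 | 14 | 1 |
| 27 | 28 | 1 |
| 40 | 41 | 29 |
| 70 | 71 | 57 |
| 86 | 87 | 85 |
| 98 | 99 | 85 |
| 111 (completer) | 112 | 85 |

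Anyone who stops before the Week 4 dispensing is recorded as 1 day. Anyone dispensed on Day 84 is recorded as 85 days, whether the last dose was on Day 84 or Day 111. Adding a constant 28 days would therefore not repair the variable.

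**Visit windows, completer, first dose Day 0.** The shortfall equals last dose day minus last dispensing day.

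- Smallest: Week 12 on Day 86, Week 16 on Day 110, last dose Day 109. 109 − 86 = 23.
- Largest on dates alone: Week 12 on Day 82, Week 16 on Day 114, last dose Day 113. 113 − 82 = 31.
- The largest case needs daily doses on Days 82 to 113, which is 113 − 82 + 1 = 32 doses from one dispensing. A blister holds 7 daily doses (protocol 10.3), but the number of blisters per visit is not stated. If 28 days were supplied (an assumption), the last dose would be on Day 82 + 27 = 109 and the shortfall 109 − 82 = 27.

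Values above 27 therefore depend on a supply of more than 28 days per visit.

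**The case against.** The strongest reply is that little depends on this. It is one descriptive table. On-schedule completers lose the same 27 days in both arms, so the formula does not by itself create a difference between arms. The rule is written in the SAP, so a careful reader could work out what 85 means. Completers and early stoppers can also be told apart elsewhere: reasons for termination (Table 14.2.3.3.1), the discontinuation listing (16.2.3), and the diary compliance and accountability listings (16.2.9.7 and 16.2.9.8). All of this stands, and it limits the weight of the point. None of those outputs gives a duration, though, so Table 14.3.1.1 stays wrong.

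One could also suppose that dispensing is a slip for dosing. The text does not allow that: the next sentence of 4.2.13 and Table 14.3.1.2 both count capsules dispensed, and elsewhere the SAP refers to first treatment or administration when it means dosing (4.2.1, 4.2.14, 4.2.15). A programmer following the text would produce 85.

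A reader might infer more than the documents support in three ways:

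- **Shortfalls of up to 31 days.** These need a supply of more than 28 days per visit, which is not stated.
- **Overstated durations, if drug is dispensed after dosing has stopped.** This is arithmetically possible but not a planned pathway. A patient who leaves the study goes to an early termination visit with the Week 16 procedures, where no drug is issued (protocol 7.5, 8.1, 8.3.6).
- **A misleading capsule table.** Section 4.2.13 does call dispensed capsules intake, but Table 14.3.1.2 is openly labelled as dispensed.

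**Conclusion.** The rule is wrong as written. Followed literally, it reports 85 days for an on-schedule completer who dosed for 112: 27 days or 24.1% short with a first dose on Day 0, and 26 days or 23.4% short with a first dose on Day 1. It also gives a patient who stopped just after Week 12 the same value as a completer. Visit windows move the completer shortfall by a few days, with anything above 27 resting on the unstated supply. Couriered supply under the COVID-19 contingency follows the same Week 4, 8 and 12 schedule (protocol Appendix 11), so it does not change the result.

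The consequence is confined to the descriptive exposure summary. A reader might suppose that a quarter of the exposure missing would distort the safety rates. It would not: the adverse event tables count patients with events and use no exposure time as denominator (SAP 7.5, protocol 12.8.4). Efficacy analyses, alpha, power and sample size do not use the variable. The correction should be made because the table's headline figure would be wrong, not because any inference is at risk.

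**What to change.** In SAP 4.2.13, replace the duration rule with: *Duration of intake = date of last dose minus date of first dose plus 1, from the compliance log or diary. If the log is not returned, the last date with evidence of dosing is used.* Show this variable in Table 14.3.1.1. For the on-schedule completer it gives 111 − 0 + 1 = 112.

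Keep Table 14.3.1.2 labelled as capsules dispensed. If capsules taken is added, derive it from the dose log, or as dispensed minus returned only where packs were actually returned. Packs that never come back should not be counted as taken; otherwise a patient lost to follow-up would appear fully dosed.

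The cost is a wording change and one re-derived variable (two if capsules taken is added), made before unblinding. Doses are already logged, and the SAP already relies on a first-treatment date for study day (4.2.1). No new data collection or study procedure is needed.

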## 8.3 Treatment Period

Following completion of a successful screening visit, patients will begin the comparative treatment period (16 weeks).

At the start of the comparative treatment period, after confirmation of continued eligibility, patients will be randomly assigned at the baseline visit (Visit 2) to one of the two treatment regimens.

Patients will be instructed to take 4 capsules of IMP which will contain either 2g DS107 or placebo. Every effort should be made to ensure IMP administration is at the same time each day. Each self-administration of IMP will be recorded in a patient compliance log.

Unscheduled visits may occur when a patient needs to make a visit in between the scheduled visit dates due to an adverse event (AE), difficulty complying with the study protocol requirements, or a significant change in their disease state. All procedures that are medically necessary should be followed.

Once patients are enrolled on the study they will be restricted from using any other treatment for AD, with the exception of emollients, as defined in Section 9.2.13.1. Any medication (prescription as well as over the counter (OTC) drugs) or therapeutic intervention deemed necessary for the patient, and which in the opinion of the Investigator do not interfere with the safety and efficacy evaluations, may be continued unless they are included in the list of 'Concomitant Medications' (Section 9.2.13).

Patients who discontinue the study early will have all study procedures scheduled for Visit 7 (see Section 8.3.6) performed as soon as possible after patient withdrawal so that all study-related information can be recorded.

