16.2.8.1	Laboratory values	SAS	Individual patient data listing of laboratory results (haematology, clinical chemistry)	L5
16.2.8.2	Laboratory values outside the normal range	SAS	Individual patient data listing of laboratory results outside the normal range	L5
16.2.9	Other Listing			
16.2.9.1	Physical examinations	SAS	Individual patient data listing by cohort and visit	L6
16.2.9.2	Medical History / Concomitant diseases	FAS	Individual patient data listing by cohort	L6
16.2.9.3	Childbearing status and Pregnancy test data	FAS	Individual patient data listing by cohort and visit	L6
16.2.9.4	Virology	FAS	Individual patient data listing by cohort	L6
16.2.9.5	ECG	FAS	Individual patient data listing by cohort and visit	L6
16.2.9.6	Study drug dispensed	SAS	Individual patient data listing by cohort and visit	L6
16.2.9.7	Patient diary compliance	SAS	Individual patient data listing by cohort and visit	L6
16.2.9.8	IMP accountability and IMP compliance	SAS	Individual patient data listing by cohort and visit	L6
16.2.9.9	Previous and Concomitant medication	FAS	Individual patient data listing by cohort	L6

16.2.9.10	Violations of inclusion/exclusion criteria	Enrolled Set (only patients with violations)	Individual patient data listing by cohort	L6
16.2.9.11	Protocol violations	SAS	Individual patient data listing by cohort	L6

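### The SAP defines intake of study medication as capsules dispensed, so no summary table shows partial adherence between dispensing visits

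*SAP*

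**What the plan says.** SAP 4.2.13 gives two derivations. For amount: "The intake of study medication will be calculated as the number of capsules dispense per visit". For duration, the figure is "calculated as day of last dispensed of study medication minus day of first dispensed of study medication plus one". Neither refers to returned capsules, the dosing log or the date of the last dose.

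SAP 7.6, under Study medication, analyses only that duration and "Number of capsules dispense", in the Safety Analysis Set. SAP Section 8 has two matching tables: 14.3.1.1 (intake duration) and 14.3.1.2, described as "Descriptive statistics of number of capsules dispensed". Two listings carry adherence data: 16.2.9.7, "Patient diary compliance", and 16.2.9.8, "IMP accountability and IMP compliance". Neither has a summary table.

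The protocol collects what a true intake figure needs. Section 10.6 says: "The patients should return all used and unused packs of IMP to the study site at every visit". Section 8.3 says: "Each self-administration of IMP will be recorded in a patient compliance log". Accountability is scheduled at Weeks 4, 8, 12 and 16 (Protocol Appendix 1), and SAP 4.1.1 places the compliance diary data in the IRT system.

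**The concern.** A count of capsules handed out shows which supplies reached the patient. It does not show what was swallowed. Calling it intake treats every returned capsule as taken.

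Three readings of the trial depend on knowing the dose received:

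- **Estimand.** The primary missing-at-random analysis is described as estimating the effect under full adherence (Protocol 12.8.2, SAP 4.1.5). A reader will want to see, by arm, how close patients came to that.
- **Null result.** The trial tests a single dose, 2 g once daily. If it shows no difference, the first question is whether patients took that dose.
- **Safety.** Protocol 1.6 reports that the most common adverse events in Phase 1 and in the Phase 2a DS107 group were gastrointestinal, and that related events were more frequent at 2 g than on placebo in Phase 2b. Lower adherence on DS107 is therefore plausible. Event rates would be read against a dispensed amount that may exceed the amount taken.

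**Working it through.** **Inputs**

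- Capsule strength 500 mg; 4 capsules once daily for 16 weeks (Protocol 10.1, 10.3).
- Dispensing at Days 0, 28, 56 and 84; none at Week 16 (Day 112); last dose the day before the Week 16 visit (Protocol Appendix 1).
- Assumption: supply equals need exactly, with no overage.
- Assumption: share of capsules returned, shown from 0% to 50%. The documents give no adherence rate.

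**Reproducing the plan's dose.** 4 x 500 mg = 2 g/day, as stated.

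**Full supply.** Doses run from Day 0 to Day 111, which is 112 days. 4 x 112 = 448 capsules, or 112 per four-week interval.

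**SAP intake against capsules taken, for a completer**

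- SAP intake = capsules dispensed = 448.
- Taken = 448 x (1 - share returned).
- Mean daily dose = taken x 0.5 g / 112.

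| Share returned | SAP intake | Taken | Mean g/day | SAP intake / taken |
|---|---|---|---|---|
| 0% | 448 | 448 | 2.0 | 1.00 |
| 10% | 448 | about 403 | 1.8 | 1.11 |
| 20% | 448 | about 358 | 1.6 | 1.25 |
| 25% | 448 | 336 | 1.5 | 1.33 |
| 50% | 448 | 224 | 1.0 | 2.00 |

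The SAP figure is the same in every row. The last row equals the daily dose of the lower Phase 2b arm (Protocol Table 1). Any overage dispensed would widen the gap.

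**Early stopper.** With a four-week supply at baseline, a patient who stops after 14 days is recorded with 112 capsules, having taken 14 x 4 = 56.

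**Whether the duration table fills the gap.** On nominal visit days a completer's duration is 84 - 0 + 1 = 85 days against 112 dosing days, 27 days (24%) short. Dividing SAP intake by SAP duration gives 448 x 0.5 / 85 = 2.64 g/day, even for a patient who took exactly 2 g/day. The two planned tables cannot be combined to recover the dose received.

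**Whether anything else in the SAP fills it.** The Per-Protocol Set has no compliance threshold (SAP 3), and the listed topics of the blind data review do not name IMP compliance (SAP 5). Protocol 12.8.1 commits to summarising plasma DGLA, but neither SAP 7.4 nor SAP Section 8 includes such an analysis.

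**The case against.** The strongest reply is that this is a labelling slip with little effect. Most of its parts are true, and they limit the point.

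- **The table is labelled honestly.** A reader might infer that a half-adherent patient will be printed as having received 2 g/day. The documents do not support that: Table 14.3.1.2 is described as a dispensing count and has no dose column. The error lies in the definition in SAP 4.2.13 and in the missing summary.
- **Early stopping is partly visible.** A reader might infer that exposure will look complete whatever patients do. Those who stop before a later dispensing visit show fewer capsules. Reasons for termination (14.2.3.3.1) and adverse events leading to discontinuation (14.3.2.5) are tabulated, by arm by default (SAP 6). A marked excess of dropouts on DS107 would show. What stays hidden is missed dosing between dispensings.
- **Adherence is not wholly unreported.** A reader might infer that under-dosing could never be distinguished from lack of effect. Listings 16.2.9.7 and 16.2.9.8 show adherence patient by patient, and trough DGLA is sampled at baseline and Weeks 4, 8 and 16. But a listing leaves the reader to build the comparison by hand, and the SAP plans no output for the trough levels.
- **No planned inference uses the variable.** The primary mixed model, the jump-to-reference analysis and the definitions of the Full and Safety Analysis Sets do not use capsule counts. This stands in full.
- **Dispensing does not depend only on attendance.** Under the COVID-19 contingency (Protocol 13.12 and Appendix 11), drug may be couriered and packs brought to the next on-site visit. Returns may therefore not be counted at every scheduled visit, and the fix must allow for that.

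**Conclusion.** The point holds as a real but modest error in exposure reporting. Under the SAP's rule, intake is wrong for any patient who returns capsules, and no summary table shows capsules taken, dose received or percent compliance.

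The possible overstatement for a completer runs from none to two-fold as the share returned goes from 0% to 50%. That range rests on exact supply and on chosen adherence levels. It shows what the rule can hide and does not predict adherence in this trial.

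The primary efficacy estimates and tests, and the adverse event counts, do not change. The loss is a by-arm view of the dose received, which supports the reading of a null result, of the full-adherence estimand and of the safety data. It should be corrected before unblinding, but it does not threaten the main analysis.

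**What to change.** 1. **SAP 4.2.13.** Define capsules taken as capsules dispensed minus capsules returned, from IMP accountability and summed over the treatment period, with the compliance log as a cross-check. Where packs are not returned, or couriered supply leaves no count, use the log. State this convention in advance.
2. **Derived variables.** Percent compliance = capsules taken / (4 x days from first to last dose, inclusive) x 100. Mean daily dose = capsules taken x 0.5 g / the same number of days (in the placebo arm, the placebo-capsule equivalent). Use dosing dates here, because the dispensing-date duration would inflate both.
3. **SAP 7.6 and Table 14.3.1.2.** Summarise capsules taken, percent compliance and mean daily dose by arm in the Safety Analysis Set. Keep the dispensed count if wanted, labelled as dispensed and not as intake.

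The planned trough DGLA summary should also be reconciled: Protocol 12.8.1 promises it and the SAP has no table for it.

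The cost is SAP wording, one reprogrammed table and a convention for unreturned packs. The data are already collected, and no visit, dose or clinical procedure changes. The downside is that reported exposure may look less favourable than a dispensing count.
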